### 5.3 Analysis of Baseline Characteristics

Demographic and baseline characteristics of the study population will be summarized overall and for each study intervention group. Variables to be summarized include, but are not limited to, age, sex, race, ethnicity, Eastern Cooperative Oncology Group (ECOG) performance status, cancer location, stage at initial diagnosis, prior lines of systemic cancer therapy, and CD8 percentage at screening.

The baseline value of any variable will be defined as the last value recorded on or before the date of first administration of study intervention.

### 5.4 Efficacy Analysis

The efficacy analysis will be based on the modified Intent-to-Treat (mITT) Population, which comprises all enrolled participants with sufficient biopsy results to be assigned to a treatment arm and who received at least one dose of study drug, unless otherwise specified. Participants will be analyzed according to the study intervention to which they were assigned.

This study is not intended or powered for hypothesis testing, including comparisons between study intervention groups. Due to the exploratory nature of this study, no control of type I error will be applied for any of the endpoints.

#### 5.4.1 Primary Efficacy Endpoints

The co-primary endpoint of CBR will be reported among all participants within each study intervention group with a 95% credible interval assuming a beta (0.4, 1.6) prior. CBR is the proportion of participants who show clinical benefit, defined as CR, PR, or SD for  $\geq 6$  months as best response by RECIST v1.1 (Eisenhauer, 2009). Per RECIST, to be assigned a best overall response of complete response (CR) or partial response (PR), changes in tumor measurements must be confirmed by a repeat assessment that should be performed no less than 4 weeks after the criteria for response are first met. The duration of SD is defined as the time from the date of first dose of study intervention until the date of radiographic disease progression per RECIST. If no radiographic progression has occurred and the most recent tumor assessment with overall response of SD occurred  $< 6$  months after the date of first dose of study intervention, the participant will not have met the SD duration criterion and will not

be considered a CBR responder. Participants who do not have a disease assessment will be counted as not having clinical benefit.

For the second co-primary endpoint, the absolute change in the percentage of CD8 cells in on-treatment biopsies from baseline will be reported with a 95% credible interval with no prior for participants in the on-treatment biopsy population. In addition, the number of participants with baseline percentage of CD8 counts < 15% who “convert” from a cold to hot tumor (any on-treatment biopsy with percentage of CD8 counts  $\geq$  15%) will be summarized. The proportion of participants who convert from cold to hot will be reported with a 95% credible interval with no prior.

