9 STATISTICAL CONSIDERATIONS

9.1 SAMPLE SIZE DETERMINATION

A total of up to approximately 200 participants with varying tumor types will be enrolled. Enrollment to initial biopsy may be about 10% higher (ie, approximately 220 participants) to account for unexpected challenges obtaining CD8 infiltration information. The selection of 200 participants is to have sufficient numbers in the CD8 high and CD8 low tumor groups in larger tumor populations to report subgroup response rates, the transformation from CD8 low to high, as well as to predict response from marker and clinical information. With 200 participants, approximately 40 and 160 participants are estimated for the CD8 high and CD8 low tumor groups, respectively (Figure 7). Clinical benefit rate (CBR) within tumor groups is expected to range from 10% to 30% (Nivolumab IB). An average CBR of 20% is assumed to provide approximately 32 participants with clinical benefit in the CD8 low tumor group. With 160 participants, a 95% credible interval of CBR with 32 responders would be (14.2%, 26.5%) assuming a beta(0.4, 1.6) prior. Similarly, if there are 30 participants in the largest disease subgroup, a 95% credible interval of response would be (8.3%, 35.2%) assuming 6 responders and a similar prior. There is no prior for the expected proportion of participants who will convert from CD8 low to CD8 high on treatment as this is a first look for this endpoint. The 95% credible interval for 16/160 (10%) participants converting would be (5.9%, 15.1%) and for 80/160 (50%) the credible interval would be (42.3%, 57.7%). Similarly, 8 of 40 participants are in the CD8 high group expected to exhibit benefit, resulting in a 95% credible interval of (9.5%, 33.2%). The selection of 200 participants allows a minimum reasonable number for estimating CBR in the CD8 high tumor group. For secondary analyses, if there are 20 responders in any CD8 status and/or tumor site group, it would be reasonable to perform multivariate logistic regression with 2 variables to predict response. Therefore, 200 participants is the smallest reasonable sample size for the initial exploration of efficacy prediction in this population.

Additional widths of credible intervals of CBR for possible subgroup sizes are presented in [Table 11](#).

Table 11: Possible Subgroup Sizes

Subgroup Size	Clinical Benefit Rate	Expected Success	95% Credible Interval
160	10	16	(6.0, 15.2)
125	10	12	(5.3, 15.5)
100	10	10	(5.1, 16.7)
75	10	8	(5.0, 18.7)

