50	10	5	(3.7, 19.9)
40	10	4	(3.2, 21.2)
30	10	3	(2.6, 23.2)
160	20	32	(14.2, 26.5)
125	20	25	(13.5, 27.4)
100	20	20	(12.9, 28.3)
75	20	15	(11.9, 29.6)
50	20	10	(10.4, 31.8)
40	20	8	(9.5, 33.2)
30	20	6	(8.3, 35.2)
160	30	48	(23.1, 37.1)
125	30	38	(22.6, 38.5)
100	30	30	(21.4, 39.0)
75	30	22	(19.6, 39.6)
50	30	15	(18.1, 42.6)
40	30	12	(16.9, 44.0)
30	30	9	(15.2, 46.0)

A total of approximately 20 advanced prostate cancer participants with CD8 low tumors will be treated with the combination of nivolumab and ipilimumab, in 1 of 2 dosing cohorts. The first 10 participants enrolled will be randomly allocated by the Sponsor into one of two cohorts (5 participants per cohort) to evaluate the safety of different dose levels of ipilimumab in combination with nivolumab. If the higher dose level (ipilimumab 5 mg/kg + nivolumab 1 mg/kg) is determined to be tolerable per [Section 6.6.1.4](#), an additional 10 participants will be enrolled at this higher dose level (Prostate Cohort B). If the safety profile of Prostate Cohort B is deemed unacceptable, an additional 10 participants will be enrolled at the lower dose level (Prostate Cohort A).

We hypothesize that higher doses of ipilimumab will demonstrate a larger proportion of participants who convert from CD8 low to CD8 high. There is no prior for the expected proportion of participants who will convert from CD8 low to CD8 high at the various dose levels of ipilimumab. With 15 participants enrolled in Prostate Cohort B, Table 12 provides 95% credible intervals for possible CD8 conversion rates in the cohort. For example, a 95% credible interval assuming 6/15 (40%) participants converting in the cohort would be (17.7%, 64.9%).

Table 12: Credible Intervals for CD8 Conversion

Subgroup Size	CD8 Conversion Rate	Expected Successes	95% Credible Interval
15	20	3	(4.7, 42.8)
15	40	6	(17.7, 64.9)
15	60	9	(35.1, 82.3)

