9.4.1 Efficacy Analyses

The efficacy analysis will be based on the modified Intent-to-Treat (mITT) Population, which comprises all enrolled participants with sufficient biopsy results to be assigned to a treatment arm and who received at least one dose of study drug, unless otherwise specified. Participants will be analyzed according to the study intervention to which they were assigned.

The primary endpoint of CBR will be reported among all participants within each study intervention group with a 95% credible interval assuming a beta (0.4, 1.6) prior. Per RECIST, to

be assigned a best overall response of CR or PR, changes in tumor measurements must be confirmed by a repeat assessment that should be performed no less than 4 weeks after the criteria for response are first met. Participants who do not have a disease assessment will be counted as not having clinical benefit. In addition, CBR and similar credible intervals will be reported for each tumor site and study intervention subgroup that has at least 10 participants.

The proportion of participants whose tumors change from CD8 low to CD8 high expression will be reported with a 95% credible interval with no prior as this is the first look.

For secondary endpoints, baseline CD8 counts will be explored for association with CBR using logistic regression models and with OS using Cox regression models. Multivariate models will be explored with up to 1 variable for every 10 events. For CBR prediction, an event is an objective response (CR or PR or SD as defined above). For association with survival, an event is a participant death.

Among the On-treatment Biopsy Population, both the baseline and on-treatment biopsies will be associated with response and survival using similar logistic and Cox regression models described above, assuming there are sufficient events to carry out the regression analyses. The association of CD8 changes from baseline to on treatment with clinical outcomes will also be explored.

The exploratory endpoint of changes in PSA (absolute and percent) from baseline will be analyzed by cohort for advanced prostate cancer participants.

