## 5 STATISTICAL ANALYSIS

Summary statistics will be presented by study intervention group. Categorical variables will be summarized using frequencies and percentages. Continuous variables will be summarized using means, standard deviations, medians, interquartile ranges (IQR; 25th to 75th percentile), minimums, and maximums.

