##### 5.4.2.1 Objective Response Rate

Objective Response Rate (ORR), is defined as the proportion of participants who attain a best overall response of CR or PR, as determined by RECIST version 1.1. Confirmation of response by a repeat tumor assessment is required for a best overall response of CR or PR. Participants without a post-baseline tumor assessment will be considered non-responders, as well as patients with a best overall response of stable disease (SD), progressive disease (PD) or not evaluable (NE).

A 95% credible interval for ORR will be calculated assuming a beta (0.4, 1.6) prior.

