#### 5.4.2.4 Association of CD8 with clinical outcomes

Several analyses will be performed to investigate the association between the percentage of CD8 cells and clinical outcomes.

- Among the participants who had tumors that converted from cold (CD8 <15%) at baseline to hot (CD8  $\geq$  15%) at any on-treatment biopsy, the following will be reported:
  - The number and proportion of patients who met ORR response criteria. A 95% credible interval will be estimated with no prior.
  - The number and proportion of patients who met CBR response criteria. A 95% credible interval will be estimated with no prior.
- Logistic regression models will be fit to assess the relationship between percentage of CD8 and clinical response (ORR and CBR). Each regression model will include an intercept term. P-values will be calculated using a Wald test to test whether the coefficient for the CD8 variable is significantly different from 0. See Table 3 for details about each regression model.

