#### 5.4.4 Subgroup Analyses

Efficacy endpoints (CBR, ORR, CD8 conversion) may be presented by tumor type if a tumor type has at least 5 participants enrolled in a treatment group.

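### The 'no prior' credible interval for CD8 conversion, and for ORR and CBR among converters, is in effect beta(0,0) and gives no interval when none or all participants have the event

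*SAP*

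**What the plan says.** SAP 5.4.1 says of the co-primary conversion endpoint: "The proportion of participants who convert from cold to hot will be reported with a 95% credible interval with no prior". Protocol 9.4.1 says that the proportion "will be reported with a 95% credible interval with no prior as this is the first look". For ORR and CBR among participants whose tumors converted, SAP 5.4.2.4 says: "A 95% credible interval will be estimated with no prior". No beta distribution is named in any of these places, and nothing is said about counts of zero or all.

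In the full groups the plan does name a prior. SAP 5.4.1 gives CBR a beta(0.4, 1.6) prior, and SAP 5.4.2.1 says: "A 95% credible interval for ORR will be calculated assuming a beta (0.4, 1.6) prior".

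On group sizes:
- SAP 5 sets the reporting unit: "Summary statistics will be presented by study intervention group".
- Protocol 9.1 allocates 5 participants to each prostate cohort and then puts all 10 additional participants into one of them, so the other stays at about 5. SAP 3 still describes 10 per arm.
- SAP 5.4.4 adds: "Efficacy endpoints (CBR, ORR, CD8 conversion) may be presented by tumor type if a tumor type has at least 5 participants".

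**The concern.** A Bayesian credible interval cannot be computed without a prior, so 'no prior' must stand for a particular one. If it stands for beta(0,0), the posterior for x events in n is Beta(x, n−x). This is a proper distribution only when both x and n−x are above zero. With no converters, or with all converting, there is nothing to take quantiles of.

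Those counts matter in small groups. A cohort with no conversions, or a converter subset with no clinical benefit, is where an upper limit tells the reader most. If no prior is named beforehand, someone will have to choose one after seeing the zero, and at these sizes the choice moves the limit materially. The plan is also uneven: ORR and CBR have a proper prior in the full groups, but not in the smaller converter subset.

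**Working it through.** **Step 1. What 'no prior' means.** The inputs are the five conversion intervals in protocol 9.1 and Table 12. The equal-tailed 95% limits are the 2.5% and 97.5% quantiles of Beta(x + a, n − x + b).

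| x/n | Printed (%) | beta(0,0) | Jeffreys (0.5,0.5) | Uniform (1,1) | beta(0.4,1.6) |
|---|---|---|---|---|---|
| 16/160 | 5.9, 15.1 | 5.86, 15.08 | 6.07, 15.36 | 6.27, 15.64 | 5.98, 15.20 |
| 80/160 | 42.3, 57.7 | 42.29, 57.71 | 42.31, 57.69 | 42.33, 57.67 | 41.97, 57.30 |
| 3/15 | 4.7, 42.8 | 4.66, 42.81 | 5.98, 44.36 | 7.27, 45.65 | 5.26, 41.35 |
| 6/15 | 17.7, 64.9 | 17.66, 64.86 | 18.75, 64.72 | 19.75, 64.57 | 16.98, 61.07 |
| 9/15 | 35.1, 82.3 | 35.14, 82.34 | 35.28, 81.25 | 35.43, 80.25 | 32.06, 77.35 |

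Only beta(0,0) reproduces all five. The 80/160 case alone does not separate it from Jeffreys or uniform. Clopper-Pearson, Wilson and Wald intervals do not match the set either; for 3/15 Clopper-Pearson gives (4.33, 48.09).

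**Step 2. How often the rule gives no interval for conversion.** P(0 or all convert) = (1 − p)^n + p^n.

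- n = 5, p = 20%: 0.8^5 + 0.2^5 = 0.3277 + 0.0003 = 32.8%.
- n = 5, p = 40%: 0.6^5 + 0.4^5 = 0.0778 + 0.0102 = 8.8%. By symmetry, p = 60% also gives 8.8%.
- n = 10 (the SAP 3 arm size): 10.7% at 20%, and 0.6% at 40% or 60%.
- n = 15: 0.8^15 = 3.5% at 20%, and 0.05% at 40% or 60%.
- n = 160: negligible at the protocol's 10% and 50% scenarios.

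For a tumor-type subgroup of 5, if the same interval is shown there, those two pooled scenarios give 0.9^5 = 59% at 10% and 2 × 0.5^5 = 6.3% at 50%.

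The n = 15 figure depends on the rate. At 10%, which the protocol uses only for n = 160, it would be 0.9^15 = 20.6%.

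**Step 3. Converter subsets.** P(no converter has benefit) = (1 − c)^k for k converters with benefit rate c. As an assumption, c = 20%, the average CBR in protocol 9.1:

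- k = 3: 0.8^3 = 51%
- k = 6: 0.8^6 = 26%
- k = 16: 0.8^16 = 2.8%
- k = 80: negligible

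If converters do better, say c = 40%, the figures for k = 3 and k = 6 fall to 0.6^3 = 21.6% and 0.6^6 = 4.7%.

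**Step 4. What a proper prior gives.** At 0/5 the upper limit is 29.7% with beta(0.4, 1.6), 37.9% with Jeffreys and 45.9% with uniform, a spread of 45.9 − 29.7 = 16.2 points. Jeffreys upper limits at other zero counts are 53.6% (0/3), 33.0% (0/6), 21.7% (0/10), 15.2% (0/15) and 14.3% (0/16).

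Where beta(0,0) already gives an interval, the largest shift on moving to Jeffreys is:
- n = 160: 0.3 point (16/160 upper limit, 15.08 to 15.36).
- n = 15, Table 12 counts: 1.6 points (3/15 upper limit, 42.81 to 44.36).
- n = 5, over 1 to 4 events: 2.7 points (2/5 lower limit, 6.76 to 9.44).

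**The case against.** The case for leaving the text alone has several parts. Beta(0,0) is a recognised limiting prior and the sponsor chose it openly because this is a first look; an analyst can apply it at every non-extreme count. The 5-per-cohort stage is there to assess safety, and the protocol illustrates conversion only at n = 15 and n = 160. SAP 5.4.4 says only that tumor-type results may be shown and promises no interval. The converter probabilities borrow the all-comer CBR, whereas the study's premise is that CD8 recruitment goes with better outcome. An interval at n = 5 says little in any case, and the study is exploratory.

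Part of this stands. Separate reporting of a cohort of 5 is inferred from the general line in SAP 5. The tumor-type figures are conditional on an interval being shown. No interval is printed for the converter subsets, so the beta(0,0) reading there rests on identical wording. The converter percentages shrink if benefit is higher among converters.

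It does not remove the point. Protocol 9.1 hypothesises more conversion at the higher ipilimumab dose, so each prostate cohort is a natural reporting unit, including the one left at about 5. The conversion endpoint uses participants with an adequate on-treatment biopsy, and those biopsies depend on medical feasibility, so denominators can only be smaller than those used here. In a study that reports estimates with intervals rather than tests, the intervals are the main output.

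The same SAP paragraph also applies 'no prior' to the absolute change in CD8 percentage. That quantity is continuous and does not fail at zero or all events, and a beta prior would not suit it; it is a separate matter.

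**Conclusion.** The concern holds as a gap in specification; no printed figure is wrong. As written, the rule gives no interval at zero or all events. At the Table 12 rates that is a 9% to 33% risk in a group of 5 and at most 3.5% in a group of 15; it is negligible at n = 160. Among converters, at an assumed 20% benefit rate, the risk of a zero count is 51% with 3 converters and 26% with 6.

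This rests on reading 'no prior' as beta(0,0), which all five printed conversion intervals support, and on the same reading for the identically worded converter analyses. No stopping rule is touched, because futility monitoring in protocol 9.3.1.2 already uses beta(0.4, 1.6). It should be corrected before the data are analysed, since the 0/5 upper limit varies by about 16 points with the prior chosen.

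**What to change.** In SAP 5.4.1 (the conversion proportion only) and SAP 5.4.2.4, replace 'no prior' with a named proper reference prior, for example Jeffreys beta(0.5, 0.5). Because the SAP supersedes the protocol, those two edits are enough.

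For consistency, make the same change in protocol 9.4.1 and restate four planning intervals in protocol 9.1 and Table 12 under Jeffreys: 16/160 (6.1, 15.4), 3/15 (6.0, 44.4), 6/15 (18.8, 64.7) and 9/15 (35.3, 81.2). The 80/160 interval (42.3, 57.7) is unchanged.

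In the conversion sentence, also state that the denominator is CD8-low participants in the On-treatment Biopsy Population, as SAP Tables 2 and 3 already imply.

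The cost is a phrase in each place. No new data are needed and no decision rule changes.

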#### 5.4.2 Secondary Efficacy Endpoints

Secondary efficacy endpoints include ORR, PFS, and OS and the association between CD8 counts and response.

##### 5.4.2.1 Objective Response Rate

Objective Response Rate (ORR), is defined as the proportion of participants who attain a best overall response of CR or PR, as determined by RECIST version 1.1. Confirmation of response by a repeat tumor assessment is required for a best overall response of CR or PR. Participants without a post-baseline tumor assessment will be considered non-responders, as well as patients with a best overall response of stable disease (SD), progressive disease (PD) or not evaluable (NE).

A 95% credible interval for ORR will be calculated assuming a beta (0.4, 1.6) prior.

##### 5.4.2.2 Progression-Free Survival

Progression-Free Survival (PFS) is defined as the time from initiation of study intervention to the date of first documented radiographic progression of disease or date of death due to any cause, whichever occurs first. Participants who continue treatment beyond initial disease progression will be considered to have progression of disease (PD) at the time of the initial progression event.

Participants who do not have radiographic PD at the time of analysis will be censored as follows:

- Participants who do not have radiographic PD and are still on study at the time of analysis will be censored at the date of the last tumor assessment documenting absence of progressive disease.
- Participants who have discontinued study treatment and have started subsequent anti-cancer therapy or had subsequent cancer surgery or radiation prior to documentation of radiographic PD will be censored at the date of the last evaluable tumor assessment prior to the initiation of subsequent treatment.

- Participants who discontinued the study prior to documentation of radiographic PD will be censored at the date of the last tumor assessment documenting absence of progressive disease.
- Participants who do not have radiographic PD and who die more than 16 weeks from their last evaluable tumor assessment will be censored at the date of the last tumor assessment documenting absence of progressive disease. Participants who die within 16 weeks of their last evaluable tumor assessment will be considered as having an event at the date of death.

PFS will be estimated using Kaplan-Meier techniques, and the median survival time and 95% CIs will be estimated within each study intervention group.

#### 5.4.2.3 Overall Survival

Overall Survival (OS) is defined as the time from initiation of study intervention until death due to any cause. Participants who are not reported as having died at the time of analysis will be censored at the most recent contact date they were known to be alive. See Section 5.8.2 for handling of missing or partial death dates.

OS will be estimated using Kaplan-Meier techniques, and the median survival time and 95% CIs will be estimated within each study intervention group.

#### 5.4.2.4 Association of CD8 with clinical outcomes

Several analyses will be performed to investigate the association between the percentage of CD8 cells and clinical outcomes.

- Among the participants who had tumors that converted from cold (CD8 <15%) at baseline to hot (CD8  $\geq$  15%) at any on-treatment biopsy, the following will be reported:
  - The number and proportion of patients who met ORR response criteria. A 95% credible interval will be estimated with no prior.
  - The number and proportion of patients who met CBR response criteria. A 95% credible interval will be estimated with no prior.
- Logistic regression models will be fit to assess the relationship between percentage of CD8 and clinical response (ORR and CBR). Each regression model will include an intercept term. P-values will be calculated using a Wald test to test whether the coefficient for the CD8 variable is significantly different from 0. See Table 3 for details about each regression model.

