## 4 STUDY CONDUCT

### 4.1 Intervention Assignment

The advanced metastatic cancer portion of this study is not randomized. Treatment assignment will be based on the percentage of tumoral CD8 cells at the initial biopsy. Participants who have a tumor with  $\geq 15\%$  CD8 cells will receive nivolumab monotherapy, and participants who have a tumor with  $< 15\%$  CD8 cells will receive ipilimumab in combination with nivolumab.

Approximately 20 advanced prostate cancer participants who have a tumor with < 15% CD8 cells will be randomly allocated to receive nivolumab 1 mg/kg in combination with ipilimumab 3 mg/kg (Prostate Cohort A) or nivolumab 1 mg/kg in combination with ipilimumab 5 mg/kg (Prostate Cohort B) in a 1:1 ratio. All advanced prostate cancer participants who have a tumor with  $\geq$  15% CD8 cells will receive nivolumab monotherapy. Participants who are randomly allocated but do not receive study intervention for any reason may be replaced. Randomization will be performed by the Sponsor.

Study intervention will be administered by site personnel and tracked using drug accountability records.

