**Table 2: Populations for Analysis**

| Population                                 | Description                                                                                                                                                                                                                      |
|--------------------------------------------|----------------------------------------------------------------------------------------------------------------------------------------------------------------------------------------------------------------------------------|
| Safety Population                          | All participants who received at least one dose of study drug. Participants will be analyzed according to the study intervention actually received.                                                                              |
| Modified Intent-to-Treat (mITT) Population | All participants with sufficient biopsy results to be assigned to a treatment arm and who received at least 1 dose of study drug. Participants will be analyzed according to the study intervention to which they were assigned. |
| On-treatment Biopsy Population             | All participants with at least 1 on-treatment biopsy with sufficient CD8 results will be included in the analyses of changes in CD8 counts.                                                                                      |

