**Table 3: Logistic Regression Model Parameters**

| Model number | Response variable (y) | Explanatory variable (x)                                                                              | Analysis Population            |
|--------------|-----------------------|-------------------------------------------------------------------------------------------------------|--------------------------------|
| 1            | CBR                   | Baseline percentage of CD8 cells                                                                      | mITT Population                |
| 2            | ORR                   | Baseline percentage of CD8 cells                                                                      | mITT Population                |
| 3            | CBR                   | Maximum percentage of CD8 cells across all on-treatment biopsies                                      | On-treatment Biopsy Population |
| 4            | ORR                   | Maximum percentage of CD8 calls across all on-treatment biopsies                                      | On-treatment Biopsy Population |
| 5            | CBR                   | Absolute change between baseline and maximum percentage of CD8 cells across all on-treatment biopsies | On-treatment Biopsy Population |
| 6            | ORR                   | Absolute change between baseline and maximum percentage of CD8 cells across all on-treatment biopsies | On-treatment Biopsy Population |
| 7            | CBR                   | CD8 Conversion Flag
(1 = CD8 converter, 0 = non-converter)                                         | On-treatment Biopsy Population |
| 8            | ORR                   | CD8 Conversion Flag
(1 = CD8 converter, 0 = non-converter)                                         | On-treatment Biopsy Population |

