## **6 DIFFERENCES COMPARED TO PROTOCOL**

The Protocol defines the secondary endpoint exploration of baseline CD8 counts association with CBR and with OS; this was removed from the SAP and will not be analyzed.

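### SAP Section 6 drops the baseline CD8–CBR analysis that Table 3 Model 1 plans, and Models 7–8 leave CD8-high participants uncoded; Models 1–2 should be labelled as marginal associations (minor)

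*SAP*

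**What the plan says.** SAP 5.4.2.4 introduces the models: "Logistic regression models will be fit to assess the relationship between percentage of CD8 and clinical response (ORR and CBR"). On their content it adds only "Each regression model will include an intercept term" and a Wald p-value for the CD8 coefficient. Table 3 then gives each model one explanatory variable. Models 1–2 use baseline CD8 percentage in the mITT Population. Models 3–6 use the on-treatment maximum, or the change to it, in the On-treatment Biopsy Population. Models 7–8 use a conversion flag in that same population, coded "1 = CD8 converter, 0 = non-converter".

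Four other places bear on these models:

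- SAP 4.1, on the metastatic portion: "Treatment assignment will be based on the percentage of tumoral CD8 cells at the initial biopsy". At 15% or above the regimen is nivolumab; below 15% it is nivolumab plus ipilimumab. Prostate participants are split between monotherapy and combination at the same cutoff.
- SAP Table 2, on the biopsy population: "All participants with at least 1 on-treatment biopsy with sufficient CD8 results will be included in the analyses of changes in CD8 counts". It is not limited by baseline CD8.
- SAP 5.4.1 counts converters within "the number of participants with baseline percentage of CD8 counts < 15"%, and 5.4.2.4 likewise describes conversion as starting from below 15%.
- SAP Section 6 describes the protocol's "exploration of baseline CD8 counts association with CBR and with OS; this was removed from the SAP and will not be analyzed".

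SAP Table 1 keeps, as a secondary objective, the association of CD8 infiltration with ORR, PFS and OS.

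**The concern.** Section 6 and Table 3 give opposite instructions about one secondary analysis. Both are in the SAP, so the rule that the SAP overrides the protocol does not settle which applies.

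For Models 7–8, two programmers could follow the SAP and fit different models. One would leave CD8-high participants out because they cannot convert. The other would code them 0 because they are not converters. The second choice mixes monotherapy participants into a comparison that is otherwise within the combination regimen.

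For Models 1–2, baseline CD8 and regimen are tied together by the assignment rule, and no arm term or by-arm fit is stated. SAP Section 2 gives the study's aim as addressing the predictive value of CD8 for selecting patients for nivolumab with or without ipilimumab. A reader could take a pooled CD8 coefficient as evidence on that aim when part or all of it is a difference between arms.

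**Working it through.** **Section 6 against Table 3.** Protocol 9.4.1 plans logistic regression of CBR on baseline CD8 and Cox regression of OS on baseline CD8. Section 6 says both are removed. Model 1 is logistic regression of CBR on baseline CD8 percentage. The OS half of Section 6 agrees with Table 3, which has no survival model; the CBR half does not. Reading counts as different from percentages does not resolve this, because SAP 5.4.1 itself speaks of a percentage of CD8 counts. The Table 1 objective still names PFS and OS, for which no association model remains.

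**Design inputs.** Protocol 9.1 expects 160 CD8-low and 40 CD8-high participants with 20% CBR in each, so 32 and 8 with benefit. The stated intervals reproduce as equal-tailed beta posteriors under the beta(0.4, 1.6) prior. Beta(32.4, 129.6) gives 14.2% to 26.5%, and Beta(8.4, 33.6) gives 9.5% to 33.2%.

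**Models 7–8, expected counts.** Assume that everyone is biopsied, 32 of 160 convert, and converter CBR is 30%; CBR across CD8-low is the plan's 20%.

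- Converters: 0.30 × 32 = 9.6 benefit, so the odds are 9.6/22.4 = 0.4286.
- CD8-low non-converters: 32 − 9.6 = 22.4 of 128 benefit, so the odds are 22.4/105.6 = 0.2121.
- CD8-high left out: OR = 0.4286/0.2121 = 2.02.
- CD8-high coded 0: their share of the reference group is 40/(128 + 40) = 24%.
  - CD8-high CBR 20%: odds (22.4 + 8)/(105.6 + 32) = 0.2209, OR 1.94.
  - CD8-high CBR 10%: odds (22.4 + 4)/(105.6 + 36) = 0.1864, OR 2.30.
  - CD8-high CBR 30%: odds (22.4 + 12)/(105.6 + 28) = 0.2575, OR 1.66.

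With 16 of 160 converting, the same steps give 1.84 with CD8-high left out, and 1.81, 2.10 or 1.58 with them coded 0 at 20%, 10% or 30%.

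**Model 1, simulation.** Trials had 160 CD8-low and 40 CD8-high participants. The outcome was drawn from the arm's CBR only, so there was no CD8 effect within either arm. The test was a two-sided Wald test at 5%. The documents give no usable CD8 distribution, so three were assumed (low/high): uniform 0–15/15–50; uniform 0–15/15–30; exponential with mean 6 truncated at 15/15 plus exponential with mean 10. Pooled rejection rates, by CBR in CD8-low/CD8-high:

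- 20%/20% (the plan's expectation): about 5%, the nominal level.
- 30%/20%: roughly 15–16%.
- 20%/30%: roughly 20–22%.
- 10%/30%: about 70–75%.

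These contrasts are assumptions inside the 10–30% CBR range that Protocol 9.1 expects across tumor groups. The result depends on the base rates as well as the gap, so other 10-point contrasts need not give the same figures. Under lognormal CD8 the three unequal contrasts gave 12–13%, 17–19% and 64–66%. Adding an arm term brought rejection back to about 4–6%. Models 2–6 were not simulated.

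**Precision of a CD8-low-only fit.** Against the pooled fit, the CD8 standard error is 1.9 to 3.0 times larger at 20%/20% and about 1.8 to 4 times larger over the contrasts listed. Under lognormal CD8 it reached 5.9 times. At an assumed true odds ratio of 1.5 per 10 CD8 points with no arm effect, power is 12–13% in CD8-low alone and 43–83% pooled.

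**The case against.** The best defence is that these models do what the SAP says they do. They estimate association, and SAP 5.4 states that the study is not intended or powered for hypothesis tests or comparisons between intervention groups and applies no type I error control. The link between CD8 and regimen comes from the assignment rule. No CD8 level receives both regimens within a portion, so no refit can show which regimen suits which CD8 level. An arm term separates CD8 from arm only through the assumed linear effect. All of that stands, and it limits the Models 1–2 point to labelling and one added estimate.

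It can also be said that the SAP organizes results by arm. The sentence in SAP 5 is "Summary statistics will be presented by study intervention group", which covers summaries, not regressions. SAP 5.4.2.2 and 5.4.2.3 state estimation within each group for PFS and OS, whereas 5.4.2.4 does not. By-arm fitting remains possible but is not stated.

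On Models 7–8, the shift at the plan's own 20% is trivial (2.02 to 1.94). That is right. The case for a change is that the coding is unspecified and one clause settles it.

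A reader might infer that the combination arm's optional progression biopsy could enter the on-treatment maximum or the flag. The documents do not support that as a gap. Protocol 4.1 limits that arm's on-treatment biopsies to two named time points and calls the progression sample optional. For the prostate combination arm, Protocol Table 4 places the optional biopsy in the end-of-treatment column.

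**Conclusion.** Two textual faults hold without any assumption. Section 6 contradicts Model 1, and Models 7–8 give no rule for participants who cannot convert. The size of the second rests on assumed conversion and benefit rates. It is negligible if CD8-high CBR is 20%, and with 32 converters it moves the odds ratio to between 1.66 and 2.30 over 10–30%.

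The Models 1–2 point holds in a limited form. As written, these are marginal associations that cannot separate baseline CD8 from regimen. A reader might go further and infer that the pooled models are biased or invalid, or that adjusting for arm would establish predictive value. Neither follows: at the plan's expected 20% in both arms nothing is distorted, and the design cannot identify predictive value for choosing a regimen under any of these fits. The simulated rates apply to Model 1 only and depend on assumed arm contrasts and CD8 distributions.

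Severity is minor. The analyses are secondary and exploratory, and neither co-primary endpoint is affected.

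**What to change.** 1. Correct SAP Section 6 to say that only the OS (Cox) association is dropped and that Model 1 is kept. Align the Table 1 association objective, which names PFS and OS, with what will be analyzed.
2. State in Table 3 that Models 7–8 are fitted in participants of the On-treatment Biopsy Population with baseline CD8 below 15%.
3. Label the pooled models as marginal associations that do not show predictive value for choosing a regimen. Beside them, report the CD8 estimate and interval from CD8-low participants alone. The metastatic portion expects about 32 CBR events there, enough for one variable under the one-per-10-events rule in Protocol 9.4.1. The CD8-high arm (about 8 events) and the CD8-low prostate participants (20 × 0.20 = 4) support description only.

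The cost is SAP wording and a few model runs on data already collected. The downside of item 3 is imprecision: the CD8-low-only fit provides an estimate with a wide interval, not a test to rely on.
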